## 5 Procedures

Approval from the Sponsor must be received prior to initiating study procedures.

Enrolled subjects (as defined in section 5.2) will undergo a pulmonary vein isolation procedure with the TactiCath SE catheter. After discharge from hospitalization post-procedure, the subject will have follow-up visits at 7 days and 30 days and 3, 6 and 12 months. Upon completion of the 12-month follow-up visit, the subject will be considered to have completed the follow-up requirements of this clinical investigation. The Principal Investigator should arrange for appropriate care of subjects following study completion.

The following sections provide a detailed description of procedures required by this CIP.

### 5.1 Informed Consent Process

The Principal Investigator or his/her authorized designee will conduct the Informed Consent Process, as required by applicable regulations and the center's IRB/EC. This process will include a verbal discussion with the subject on all aspects of the clinical study that are relevant to the subject's decision to participate, such as details of clinical study procedures, anticipated benefits, and potential risks of clinical study participation. During the discussion, the Principal Investigator or his/her authorized designee will avoid any improper influence on the subject and will respect the subject's legal rights. The subject shall be provided with the informed consent form written in a language that is understandable to the subject and has been approved by the center's IRB/EC. The subject shall have adequate time to review, ask questions and consider participation. No study procedures will occur until subject consent is obtained. The template informed consent is provided under separate cover.

If the subject agrees to participate, the Informed Consent form must be signed and dated by the subject and by the person obtaining the consent. The signed original will be filed in the subject's hospital or research charts, and a copy will be provided to the subject.

The Principal Investigator or his/her authorized designee will document the informed consent process in the subject's hospital and/or research charts. The date of signature will be entered on an applicable electronic Case Report Form (eCRF).

Failure to obtain informed consent from a subject prior to a study specific procedure should be reported to Sponsor within 5 working days and to the reviewing center's IRB/EC according to the IRB's/ EC's reporting requirements.

If, during the clinical investigation, new information becomes available that can significantly affect a subject's future health and medical care, the Principal Investigator or his/her authorized designee will provide this information to the subject. If relevant, the subject will be asked to confirm their continuing informed consent in writing.

## 5.2 Point of Enrollment

A subject is considered enrolled in the clinical trial from the moment the subject has provided written informed consent.

The Principal Investigator or delegated study personnel will record enrollment information (name of the clinical investigation, date of consent and Inclusion/exclusion information) in the hospital records and complete and submit an applicable eCRF in a timely manner.

Notification of enrollment to the Sponsor is considered to have occurred when the Sponsor has received the applicable eCRF.

## 5.3 Scheduled Procedures

The Principal Investigator is responsible for ensuring all clinical investigation data is collected as required per CIP scheduled procedures. Physical exams, including the neurological assessment, must be performed by a physician. NIH Stroke Scale must be administered by a certified assessor.

### 5.3.1 Baseline

The following assessments and information will be collected at the baseline visit.

- Document the informed consent process
- Confirm enrollment criteria
- Subject demographics
- Complete medical history, cardiac arrhythmias and documentation of PAF
- Complete QOL (EQ-5D-5L & AFEQT)
- Complete physical exam (including neurological assessment), NIH Stroke Scale (NIHSS) assessment, ECG, & NYHA assessment. NOTE: If these were done as standard of care prior to consent, they may be used if they were done within 30 days prior to index ablation procedure. Subjects with new findings on the neurologic assessment/NIHSS are required to have a formal neurological consult and follow-up diffusion-weighted MR imaging of the brain. If contra-indicated for MR, then an alternate form of imaging may be performed. Subjects should also be re-evaluated against the inclusion/exclusion criteria to ensure they are still eligible.
- A urine pregnancy test should be performed for women of child-bearing potential.
- Document anti-arrhythmic drug (AAD) history, including maximum ineffective dosages and anticoagulant usage
- Assessment for atrial thrombus must be performed within one day of the ablation procedure. Standard of care may be used for this assessment. It is recommended that transesophageal echocardiography (TEE) be performed prior (within 1 day) to the index ablation procedure to identify any left atrial thrombus. In case of a finding of atrial thrombus, the procedure will not

be scheduled and the subject placed on anticoagulation until freedom from thrombus can be confirmed. They may be rescreened once provided it is within 90 days of initial consent.

It is recommended to follow pre-ablation anticoagulation guidelines from the 2017 HRS/EHRA/ECAS/APHRS/SOLAECE Expert Consensus Statement on Catheter and Surgical Ablation for Atrial Fibrillation

Any subjects who do not meet inclusion/exclusion criteria prior to the insertion of the TactiCath SE into their vasculature will be exited from the trial.

### 5.3.2 Ablation Procedure

The ablation procedure will be performed no more than 14 days after consent. This section describes the activities performed and information collected at the ablation procedure visit.

- The procedure should be performed following the Instructions for Use.
- It is strongly recommended that a strategy of uninterrupted anti-coagulation be in place for peri-operative management.
- It is strongly recommended that vascular access be obtained using ultrasound to minimize complications.
- It is recommended that heparin be administered prior to or immediately following transeptal puncture during AF catheter ablation procedures and adjusted to achieve and maintain an ACT of at least 300 seconds. Administration of protamine following AF catheter ablation to reverse heparin is acceptable.
- If assessment for presence of atrial thrombus was not performed prior to the initiation of the ablation procedure, an intracardiac echocardiography (ICE) or TEE assessment must be performed at the time of the procedure to exclude atrial thrombus. In case of a finding of atrial thrombus, the procedure will be postponed and the subject placed on anticoagulation until freedom from thrombus can be confirmed. They may be rescreened once provided it is within 90 days of initial consent.
- If no atrial thrombus is found, a standard treatment scheme of mapping and ablation will be conducted during the interventional procedure. It is required that confirmation of entrance block be performed.
- In the absence of a clinical or induced arrhythmia, additional ablation lesion sets (e.g., prophylactic linear lesions, ablation of CFAE sites, etc.) should not be performed.
- Subjects will receive ablations to achieve pulmonary vein isolation (PVI). The recommended ablation parameters are as follows:
  - Power (10-30W)
  - Contact force (target 20 g, 10-30 g)
  - Temperature (37 – 50 °C)
  - Irrigation flow rate (17 - 30 ml/min)
- In addition to PVI, subjects with documented atrial flutter, AT or other SVT (spontaneous or induced) may undergo additional targeted ablation as clinically indicated.
- For subjects who receive cavotricuspid isthmus (CTI) ablation for typical atrial flutter, It is required that bi-directional block be re-confirmed 30 minutes after initial block is achieved.
- Consistent with data published in the 2017 HRS/EHRA/ECAS/APHRS/SOLAECE Expert Consensus Statement on Catheter and Surgical Ablation for Atrial Fibrillation, the following standard of care peri-procedure precautions are strongly recommended to minimize risks to subject safety:
  - Esophageal temperature monitoring – it is strongly recommended that esophageal temperature be monitored using an esophageal temperature probe at the anatomical location nearest the site of energy delivery. An alternative is esophageal deviation.
  - Termination of energy is strongly recommended if a >1°C rise in esophageal temperature is observed.

- Intracardiac echocardiography (ICE) – use of a phased-array ICE probe during the procedure to guide septal puncture and to monitor catheter position and manipulation is strongly recommended.
- Use of robotic systems to assist in the procedure is not allowed.
- Please refer to the catheter's IFU for further details.
- PVI must be documented and verified via entrance block with a multipolar catheter at or beyond 30 minutes from the last ablation lesion for each vein.
- Use of adenosine and / or isoproterenol is acceptable to assist in finding gaps.
- Cardioversion is allowed after PVI to assist with checking for isolation.
- The data from the entire procedure recorded on the commercial EnSite system should be anonymized and backed up on a USB drive and sent to the sponsor within reasonable timelines.
- It is strongly recommended that the operator personally evaluates the subject on the evening of the procedure as well as on the following morning, and maintains active surveillance of the subject's postoperative care and condition.

If for any reason the subject has the TactiCath SE inserted into their vasculature, but no ablation is performed, the subject will be followed up for 30 days to assess safety, then exit the trial.

#### **Post Ablation Anticoagulation Strategy**

The following recommendations are adapted from the 2017 HRS/EHRA/ECAS/APHRS/SOLAECE Expert Consensus Statement on Catheter and Surgical Ablation for Atrial Fibrillation:

- In patients who are not therapeutically anticoagulated prior to catheter ablation of AF and in whom warfarin will be used for anticoagulation post ablation, low molecular weight heparin or intravenous heparin should be used as a bridge for initiation of systemic anticoagulation with warfarin following AF ablationa.
- Systemic anticoagulation with warfarina or novel oral anticoagulation (NOAC) is recommended for at least 2 months post catheter ablation of AF and systemic anticoagulation beyond 2 months post ablation should be based on the patient's stroke risk profile and not on the perceived success or failure of the ablation procedure.
- Adherence to AF anticoagulation guidelines is recommended for patients who have undergone an AF ablation procedure, regardless of the apparent success or failure of the procedure.
- In patients who have not been anticoagulated prior to catheter ablation of AF or in whom anticoagulation with a NOAC or warfarin has been interrupted prior to ablation, administration of a NOAC 3 to 5 hours after achievement of hemostasis is reasonable post ablation.

#### **5.3.3 Pre-Discharge Procedure**

The following post-treatment evaluations will be performed within 72 hours (or as indicated) after the treatment procedure and before discharging the subject:

- TTE within 24 hours post-procedure is recommended to document absence of pericardial effusion.
- Complete physical exam (including neurological assessment).
- Complete NIH Stroke Scale (NIHSS) assessment (must be done at hospital discharge or 24±12 hours after the procedure, whichever is later). Subjects with new findings on the neurologic assessment are required to have a formal neurological consult and follow-up

---

a Time in therapeutic range (TTR) should be > 65%-70% on warfarin.

diffusion-weighted MR imaging of the brain. If contra-indicated for MR, then an alternate form of imaging may be performed.

- Document AAD and anti-coagulant usage.
- Document adverse events and protocol deviations.

#### 5.3.4 Scheduled Follow-ups

Subjects will undergo the following assessments described below at 7 and 30 days, and at 3, 6 and 12 months post ablation procedure.

##### 7-Day (7 ± 2 days) Follow-up

- Complete physical exam (including neurological assessment).
- Complete NIHSS. Subjects with new findings on the neurologic assessment are required to have a formal neurological consult and follow-up diffusion-weighted MR imaging of the brain. If contra-indicated for MR, then an alternate form of imaging may be performed.
- Document adverse events and protocol deviations.
- Document anti-arrhythmic and anti-coagulant drug usage.
- If there are symptoms present that suggest pulmonary vein stenosis (e.g. shortness of breath, cough, and hemoptysis), complete CT or MRI imaging of pulmonary veins.

##### 30-Day (30 ± 7 days) Follow-up

- 12-lead ECG
- Document adverse events and protocol deviations.
- Document anti-arrhythmic and anti-coagulant drug usage.
- If there are symptoms present that suggest pulmonary vein stenosis (e.g. shortness of breath, cough, and hemoptysis), complete CT or MRI imaging of pulmonary veins.

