## 4 Clinical Investigation Design

### 4.1 Clinical Investigation Design

This is a prospective, multi-center, single-arm clinical trial to demonstrate the acute safety and effectiveness of the TactiCath SE catheter for the treatment of PAF against a performance goal. One hundred fifty six (156) subjects will be enrolled at up to 35 investigational sites in the US, Europe, and Australia. Only sites that enroll at least one subject will be part of the analysis population. No center may contribute more than 20% of the total number of enrollments without sponsor pre-approval to exceed this proportion and at least 50% of subjects must be from the United States.

[REDACTED] Subjects will be followed for 12 months after the index ablation procedure and then exit the clinical trial. [REDACTED]

[REDACTED] The pre-market approval (PMA) clinical report will be submitted when at least 140 subjects have been enrolled, had the investigational catheter inserted into their vasculature, and either experienced an event as defined in section 4.3.1, completed their 30 day follow up visit, or have been lost to follow up per section 5.7.

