#### 4.3.1 Primary Safety Endpoint

The primary safety endpoint is the rate of device or procedure-related serious adverse events occurring within 7 days of the index procedure. SAEs related solely to arrhythmia recurrence (without coexisting conditions such as thromboembolism, worsening heart failure, etc.) will not be considered primary safety endpoint events. The SAEs that will be included in this endpoint are:

- Atrial-esophageal fistula
- AV block
- Cardiac perforation/ Tamponade
- Death
- Diaphragmatic paralysis
- Gastroparesis
- Hospitalization
- Myocardial Infarction
- Pericarditis
- Pneumothorax
- Pulmonary edema
- Pulmonary vein stenosis
- Stroke
- Thromboembolism
- Transient ischemic attack
- Vascular access complication

These events must meet the criteria listed in Appendix C to be included in the primary endpoint as adjudicated by the clinical events committee (CEC). Atrial-esophageal fistula, cardiac perforation/tamponade, and pulmonary vein stenosis that occur >7 days post procedure through 30 days will also contribute to the primary endpoint.

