**Table 2 List of all clinical investigation specific tests and activities**

Study Activity	Enrollment/ Baseline	Procedure (within 14 days of consent)	Pre- Discharge	7-Day Visit (± 2 days)	30-Day Visit (± 7 days)	3-month Visit (± 14 days)	6-month Visit (± 21 days)	12-month Visit (± 21 days)
Eligibility Check	X							
Informed Consent Process	X							
Demographics / Medical History	X							
Physical Examination (including neurological assessment)	X		X	X				
NIHSS	X		X	X				
Diffusion-weighted MRI - Brain	(X)		(X)	(X)				
CT or MRI of pulmonary veins				(X)	(X)		(X)	(X)
Urine pregnancy test	(X)							
NYHA	X							
Record Antiarrhythmic / Anti- coagulant Medication	X		X	X	X	X	X	X
Confirm absence of thrombus (per standard of care)**	X	(X)						
Ablation procedure		X						
Trans thoracic echocardiogram		X*						
Trans telephonic monitoring***						X	X	X
12-Lead ECG	X				X	X	X	X
24-hour Holter-monitoring								
QOL (EQ-5D-5L & AFEQT)	X					X	X	X
Adverse Events	(X)	(X)	(X)	(X)	(X)	(X)	(X)	(X)
Deviation	(X)	(X)	(X)	(X)	(X)	(X)	(X)	(X)
Withdrawal	(X)	(X)	(X)	(X)	(X)	(X)	(X)	(X)
Health Care Utilization				(X)	(X)	(X)	(X)	(X)

(X) if applicable

\*Recommended post procedure to exclude pericardial effusion.

\*\*Must be done within one day of procedure (day of or day prior to).

\*\*\*Collected monthly and whenever symptoms are present from 3 to 12 months post ablation procedure.

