### 6.5 Timing of Analysis

The primary endpoint analysis will be performed and the pre-market approval (PMA) clinical report will be submitted when 140 subjects have data available to assess the primary safety and effectiveness endpoints.

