### 5.1.2 Analysis Methodology

The primary safety endpoint event rate will be calculated based on the number of subjects experiencing a primary safety endpoint divided by the total number of subjects in the analysis population. The null hypothesis will be rejected if the upper bound of the one-sided 95% exact binomial confidence interval for the proportion of subjects with the primary safety endpoint is less than 0.162. Subjects who terminate the study prematurely without experiencing any primary safety endpoint events will be excluded.

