### 5.1.4 Analysis Population

The analysis population for this endpoint will include all enrolled subjects who have also had the TactiCath SE inserted into their vasculature, and either had an event or completed a visit at or beyond their 30-day follow up visit window. Subjects without an event that are lost to follow up without a visit at or beyond their 30-day follow up visit window will be excluded from this analysis.

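### An event-free subject becomes evaluable for the primary safety endpoint from day 23, although three components count through day 30; a few late events could be absent at data lock

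*Protocol*

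**What the plan says.** - **Endpoint.** Most components of the primary safety endpoint count within 7 days of the index procedure. Protocol 4.3.1 extends the period for three of them: "Atrial-esophageal fistula, cardiac perforation/tamponade, and pulmonary vein stenosis that occur >7 days post procedure through 30 days will also contribute to the primary endpoint". SAP 4.1 repeats the rule.
- **Visit window.** Protocol 5.3.4 sets a "30-Day (30 ± 7 days) Follow-up", and Table 2 carries the same tolerance.
- **Evaluability.** Protocol 6.1.1.3 and SAP 5.1.4 admit catheter-inserted subjects who "either had an event or completed a visit at or beyond their 30-day follow up visit window". Neither asks for status to be known through day 30.
- **Premature termination.** SAP 5.1.2 adds: "Subjects who terminate the study prematurely without experiencing any primary safety endpoint events will be excluded". It gives no time point.
- **Trigger.** In protocol 4.1 (and SAP 3) the report is submitted once at least 140 subjects had an event, "completed their 30 day follow up visit, or have been lost to follow up per section 5.7". Protocol 6.5 and SAP 5.6 place the analysis "when 140 subjects have data available to assess the primary safety and effectiveness endpoints".
- **Later capture.** Protocol 8.2 continues safety surveillance until the subject's participation ends and requires SAEs within 3 calendar days of site awareness. The 3-month visit (90 ± 14 days) again documents adverse events and prompts for symptoms of pulmonary vein stenosis.

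**The concern.** The period over which the endpoint is defined and the contact that qualifies a subject as a non-event do not match. A visit on day 23 satisfies the denominator rule while a week of the late-component period is still to come. The trigger counts visits and not elapsed days, so the last subjects counted towards 140 may be younger than day 30 when the data are cut.

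The error runs in one direction. An uncounted late event makes a true event a non-event, which lowers the observed rate and favours passing. It concerns the complications for which the endpoint was extended. The tipping-point analysis in SAP 5.1.6 does not cover it, because that analysis imputes only subjects who leave the study early. A subject seen on day 23 who stays in the trial is analysed as a complete non-event.

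**Working it through.** The safety sample-size text is redacted, so there is no stated N or power to reproduce. The check concerns timing and the decision boundary.

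**1. Window arithmetic.** The visit window is 30 − 7 = day 23 to 30 + 7 = day 37. The late-component period is days 8 to 30, which is 23 days. A day-23 visit leaves days 24 to 30, or 7 days (7/23 = 30%). A day-29 visit leaves 1 day.

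**2. Decision boundary.** The test is exact binomial, one-sided 0.05, against 16.2% (protocol 6.1.1). The exact upper bound for x events in n is the 95th percentile of Beta(x + 1, n − x).

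| n = 140 | Rate | Upper bound | Result |
|---|---|---|---|
| 15 events | 10.7% | 16.02% | pass |
| 16 events | 11.4% | 16.84% | fail |

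The exact type I error is 0.0445 with a limit of 15, and would be 0.0737 with a limit of 16. Pass limits at other sizes are 13 of 130, 16 of 150 and 17 of 156.

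**3. How many subjects are exposed at lock.** The documents give no enrolment rate, visit distribution or lock lag. Assume even enrolment of 140 subjects, visits spread evenly over the 15 days from 23 to 37, and lock on the trigger day. Let r be subjects treated per day.

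- *Seen, but not yet at day 30.* At age a (23 to 29 days) the share already seen is (a − 22)/15. The sum is (1 + 2 + … + 7)/15 = 28/15, so the count is 28/15 × r.
- *Past day 30, seen on days 23 to 29, with the 3-month window not yet open.* That window opens on day 90 − 14 = 76. Ages 30 to 75 are 46 days, and 7/15 of these subjects were seen early, so the count is 46 × 7/15 × r = 21.5r. These subjects are under SAE reporting but have had no scheduled enquiry since their early visit.

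| Enrolment period | r | Under day 30 | Past day 30, no later scheduled contact |
|---|---|---|---|
| 3 months (91 days) | 1.54 | 2.9 | 33 |
| 6 months (183 days) | 0.77 | 1.4 | 16 |
| 12 months (365 days) | 0.38 | 0.7 | 8 |

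Only the first group has a truncated observation period. The second loses an event only if the site has not learned of it by lock.

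**4. What a miss would do.** Suppose a share m of all subjects has a first qualifying event that goes uncounted (assumed values). At a true rate of 16.2%, the chance of passing is the binomial probability of at most 15 events in 140 at rate 16.2% − m.

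| m | Expected missed events (140m) | Chance of passing |
|---|---|---|
| 0 | 0 | 4.4% |
| 0.25% | 0.35 | 5.2% |
| 0.5% | 0.7 | 6.1% |
| 1% | 1.4 | 8.2% |

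For scale, under 3-month enrolment, 0.35 missed events would need 0.35/2.9 = 12% of the truncated group to have such an event in the remaining days. Across both groups it would need 0.35/(2.9 + 33) = 1.0% to have one that was still unknown at lock. The first figure looks high for events in at most 7 days. The documents do not allow either to be confirmed or excluded.

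**5. Adjacent inconsistency.** Take a subject seen on day 23 who withdraws event-free on day 25. SAP 5.1.2 excludes this subject, while SAP 5.1.4 keeps the subject because an in-window visit was completed.

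**The case against.** A reader might infer that an early visit closes the subject as event-free. On that reading, with visits spread evenly, 7/15 = 47% of subjects would lose 4 days of endpoint observation on average. The documents do not support this. Events count by when they occur; the visit only decides whether an event-free subject enters the denominator. Surveillance is continuous, SAEs are due within 3 calendar days of awareness, the 3-month visit asks again, and the clinical events committee makes the final determination. A tamponade on day 27 after a visit on day 25 is still a primary event. The 47% and the 4 days describe visit timing, not missing data, and the 30% is a share of days for a day-23 visit, not a share of events.

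It is also fair to say that one event deciding the result is true of any exact test at its boundary and does not show that this rule causes a miss. Protocol 6.5 and SAP 5.6 require data sufficient to assess the endpoint, which could be read as data through day 30. Redacted text near the trigger and in the sample-size sections may contain a data-cut rule.

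What remains is narrower. No visible text states a day-30 requirement or a lag before lock. SAE reporting depends on the site becoming aware. Pulmonary vein imaging is prompted by symptoms, so an early visit also moves that check before day 30. No planned sensitivity analysis covers subjects seen early who remain in the trial.

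**Conclusion.** The mismatch is real, and its severity is minor. The evaluability rule and the trigger permit a non-event to be counted before the endpoint period has ended, and any resulting error lowers the safety event rate. Such events are not lost to the trial. They can be absent from the primary analysis only for subjects seen on days 23 to 29 who, at lock, are younger than day 30 or have had no later contact. The group with a truncated period is about 1 to 3 subjects under even enrolment over 3 to 12 months with no lock lag, which is an assumption. The number of missed events cannot be estimated from the documents and is probably small. It would matter if the count fell at the boundary of 15 against 16 in 140. A data-cut rule in the redacted text would settle the point and would need only to be cited.

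**What to change.** - Leave the visit window unchanged.
- In protocol 6.1.1.3 and SAP 5.1.4, count an event-free subject as evaluable only when adverse event status is documented on or after day 30, by the 30-day visit, a telephone contact or a later visit.
- Put the same condition into the 140-subject trigger (protocol 4.1 and 6.5, SAP 3 and 5.6).
- Treat event-free subjects without such documentation as missing in the tipping-point analysis (SAP 5.1.6), and align SAP 5.1.2 with this, which also resolves the withdrawal case in step 5 of the working.

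**Cost.** Wording changes in both documents, and a short contact for subjects seen on days 23 to 29 who have no later visit by lock. Under the even-spread assumption, at most 140 × 7/15 = about 65 subjects need one. The data cut may move by up to about a week. The test, the performance goal and the pass limit for a given n do not change.
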